This document contains proprietary and confidential information of Levita Magnetics. Do not copy, dis tribute, or share with others without prior written authorization from Levita Magnetics.		8

Protocol Synopsis

Sponsor	Levita Magnetics
Protocol Title	Prospective, multi-center, single-arm, open label study designed to assess the safety and feasibility of Liver Retraction with the Levita Magnetic Surgical System: Extended Magnetic Grasper Device
Protocol Number	LVT009
Investigational Device	Magnetic Surgical System: Extended Magnetic Grasper Device
Device Description	Compared to the Magnetic Surgical System (MSS) that is cleared for market in the U.S. per 510(k) K223673 and commercially available in Chile, the investigational device (MSS Version 2) comprises the same external Magnetic Controller and a modified version of the cleared Magnetic Grasper Device with a longer Grasper Tip (12.5 cm compared to 6.5 cm).
Study Objective	The purpose of this study is to evaluate the safety and effectiveness of the Extended Magnetic Grasper Device in patients undergoing bariatric and/or hiatal hernia procedures, as a liver retractor grasping the liver and/or the tissue surrounding the crus of the diaphragm.
Study Design	Prospective, multi-center, single-arm, open label study.
Enrollment Size and Number of Sites	Up to 30 subjects will be competitively enrolled in up to 3 clinical sites in Chile.
Subject Population	All patients at least 18 years of age presenting for elective bariatric and/or hiatal hernia surgery are potential candidates.
Rationale	Levita has developed an alternative system to provide liver retraction with a Version 2 of the Magnetic Grasper Device that can be attached to the liver or the tissue surrounding the crus of the diaphragm.

LVT009 Revision: B Date: 19 Jun 24	CONFIDENTIAL	Page 6 of 39
This document contains p	roprietary and confidential information of	Lovita Magnetics

Safety Outcomes	All adverse events will be captured and reported. Adverse
	events will be summarized by relatedness to the device and/or procedure, seriousness and level of severity.
Feasibility Outcomes	Ability to adequately mobilize the liver to achieve an effective exposure of the target tissue. Adequate mobilization is not achieved if it is necessary to use another liver retractor during the procedure.
Inclusion Criteria	 Participants must meet ALL of the following inclusion criteria to be eligible for participation in the study: At least 18 years of age. Scheduled to undergo elective bariatric and/or hiatal hernia procedures. Willing and able to provide a written Informed Consent Form (ICF) to participate in the study prior to any study required procedures.
Exclusion Criteria	 Subjects must be EXCLUDED from participation in this study if ANY of the following exclusion criteria are met: Individuals with pacemakers, defibrillators, or other electromedical implants. Individuals with ferromagnetic implants. American Society of Anesthesiologists (ASA) score of III or IV. Significant comorbidities: cardiovascular, neuromuscular, chronic obstructive pulmonary disease, and urological disease (renal failure). Clinical history of impaired coagulation confirmed by abnormal blood tests. Individuals has signs of hepatic abnormality (e.g.: cirrhosis, liver failure, increase in liver enzymes, etc.). Anatomical abnormality or disease of intended target tissue noted after initiation of index procedure that would prevent device use. Pregnant or wishes to become pregnant during the length of study participation. Individual is not likely to comply with the follow-up evaluation schedule. Participating in a clinical trial of another investigational drug or device. Prisoner or under incarceration.

LVT009 Revision: B Date: 19 Jun 24	CONFIDENTIAL	Page 7 of 39
This document contains pr	oprietary and confidential information of	f Levita Magnetics

Study Duration / Follow-up Period	Subjects will be followed for 30 days post-procedure, with follow-up visits at hospital discharge, 7 days, and 30 days post-procedure.
Clinical Sites* and Site Principal Investigators*	[name] Hospital Luis Tisné Santiago, Chile
	[name] Clínica Colonial Santiago, Chile
	[name] Clínica INDISA Santiago, Chile
Medical Expert	[name] Chief of Bariatrics and Metabolic Surgery Duke University, Durham, NC, USA

*Additional Investigators and Clinical Sites will be listed in a study report or separate document.

LVT009 Revision: B Date: 19 Jun 24	CONFIDENTIAL	Page 8 of 39
This document contains proprietary and confidential information of Levita Magnetics.		
Do not copy, dis tribute, or share with others without prior written authorization from Levita Magnetics.		

Table of Contents

1./		IISTRATIVE INFORMATION	2
1.1	COI	NTACTS	2
2.	ABB	REVIATIONS / ACRONYMS	11

2. ABBREVIATIONS / ACRONYMS

Abbreviations	Definitions
AE	Adverse Event
CFR	Code of Federal Regulations
CRF	Case Report Form
EC	Ethics Committee
Ext	Extended
FDA	Food and Drug Administration
GCP	Good Clinical Practice
GDP	Good Documentation Practice
HIPPA	Health Insurance Portability and Accountability Act
ICF	Informed Consent Form
ICH	International Council for Harmonization
IFU	Instructions for Use
IRB	Institutional Review Board
ISO	International Organization for Standardization
LOS	Length of Stay
MC	Magnetic Controller
MGD	Magnetic Grasper Device
MIS	Minimally Invasive Surgery
MSS	Magnetic Surgical System
N/A	Not Applicable
N/D	Not Done
OR	Operating Room
PACU	Post Anesthesia Care Unit
PD	Protocol Deviation
PI	Principal Investigator
PP	Per Protocol
SADE	Serious Adverse Device Effect
SAE	Serious Adverse Event
SD	Standard Deviation
SDV	Source Document Verification
SOC	Standard of Care
SOP	Standard Operating Procedures
UADE	Unanticipated Adverse Device Effect

LVT009 Revision: B Date: 19 Jun 24	CONFIDENTIAL	Page 11 of 39
This document contains proprietary and confidential information of Levita Magnetics.		
Do not copy, dis tribute, or share with others without prior written authorization from Levita Magnetics.		

3. INTRODUCTION

3.1 Background and Rationale

Since the introduction of minimally invasive surgery (MIS) in the 1980's, laparoscopy has become the preferred approach for most intra-abdominal procedures. One of the key components of laparoscopic surgery, of any surgery for that matter, is the ability to achieve and maintain adequate visualization of the surgical target throughout the procedure. During certain MIS procedures, the patient's internal organs, such as the liver, can block or obscure the surgical view. A number of surgical instruments (retractors) have been developed to help mobilize abdominal organs to obtain an adequate surgical view during MIS procedures. Most of these instruments require an additional abdominal wall puncture/incision to use them, leading to potentially increased risk of postoperative pain and additional scars, as well as incision-related complications such as injury to major blood vessels and bowel, infection, incision-related hernias, scarring and chronic incisional pain. The interest in less invasiveness in surgery is aimed at reducing the number of abdominal incisions, providing less postoperative pain, reducing the risk of incision-related complications, improving the cosmetic results, and increasing overall patient satisfaction after surgery (Nguyen et al).

Levita Magnetics International Corp. has developed the Levita® Magnetic Surgical System (MSS) that can be used for tissue/organ mobilization and does not require an additional abdominal wall puncture/incision. The MSS is comprised of a Magnetic Grasper and an external Magnetic Controller. The Magnetic Grasper Device is compatible with a 10 mm laparoscopic port. The Magnetic Grasper Device is placed internally during laparoscopic surgery and is mobilized by the external magnetic field of the Magnetic Controller through the abdominal wall.

When used for liver mobilization, the Magnetic Surgical System delivers and attaches its Detachable Grasper tip to the liver border. The handle portion of the Magnetic Grasper Device is then removed from the body, leaving the Detachable Grasper attached to the liver and the introduction port available for use by another instrument. With the Detachable Grasper attached to the liver, the external Magnetic Controller is placed external to the abdominal wall, thereby attracting the Detachable Grasper for the purposes of liver mobilization. The Magnetic Controller can then be moved freely, facilitating unrestricted shaft-less tissue mobilization. At the end of the procedure, the Detachable Grasper Device handle and removed from the patient.

The safety and effectiveness of the Levita Magnetic Surgical System has been demonstrated in multiple studies (Rivas et al, Haskins, et al, Luengas et al, Welsh et al, Davis et al) and is FDA cleared for liver retraction in bariatric procedures.

LVT009 Revision: B Date: 19 Jun 24	CONFIDENTIAL	Page 12 of 39
This document contains p	roprietary and confidential information or	^f Levita Magnetics.

Nevertheless, the current system can present some limitations when a clear exposure of the hiatus is needed. In order to overcome that limitation, a Version 2 of the Grasper Tiphas been developed with a longer total length. Whereas the original Grasper Tip of the Magnetic Grasper Device is 6cm long, the Version 2 Grasper Tip is 12.5cm long. This will enable retraction of the liver in a different way in that Version 2 not only grasps the liver, but also may be used to grasp the tissue surrounding the crus of the diaphragm for increased retraction of the liver for better exposure of the target tissue.

This current study is intended to evaluate the safety and effectiveness of this new version of the Magnetic Surgical System for liver mobilization and expand the understanding of the Magnetic Surgical System as a tool for less invasive surgery.

4. SURGICAL SYSTEM DEVICE DESCRIPTION

The Levita Magnetic Surgical System (MSS) is composed of two handheld instruments: a Magnetic Grasper Device and an external Magnetic Controller. The Magnetic Grasper Device (**Figure 1**) is comprised of two main components: a Detachable Grasper and a Delivery/Retrieval Shaft. Once the Magnetic Grasper Device is inserted through an access port and the Grasper is attached to the desired tissue, the Detachable Grasper can be detached from the Delivery/Retrieval Shaft and controlled externally using the Magnetic Controller. Traction of the tissue is maintained through the magnetic field attraction between the Detachable Grasper and the Magnetic Controller. The Magnetic Grasper Device is compatible with a \geq 10 mm laparoscopic port. The Magnetic Grasper Device is single-use, disposable, and provided sterile to the user.

[figure not shown]

Figure 1. Magnetic Grasper Device

LVT009 Revision: B Date: 19 Jun 24	CONFIDENTIAL	Page 13 of 39	
This document contains proprietary and confidential information of Levita Magnetics.			
Do not copy, dis tribute, or share with others without prior written authorization from Levita Magnetics.			

The Magnetic Controller (Figure 2) is a single unit with handles that is held external to the body and emits a magnetic field that attracts the Detachable Grasper. Once the Detachable Grasper is attached to the desired tissue and detached from the Delivery/Retrieval Shaft, the Magnetic Controller is placed external to the body to magnetically attract the Detachable Grasper to manipulate the target tissue. Adjusting the distance between the Magnetic Controller and the Detachable Grasper will modulate the magnetic attraction used for tissue retraction/manipulation. If desired, the user can connect the Magnetic Controller to a commercially available surgical support arm that is compatible with a hexagonshaped mounting stem or connected to a surgeon controlled arm (MARSTM) system). The external Magnetic Controller is re-usable, provided non-sterile to the user, and must be placed in an off-the-shelf sterile bag prior to use.

[figure not shown]

Figure 2. Magnetic Controller

The Magnetic Grasper Device is actuated via its handle with two distinct scissortype motions to open and close the Detachable Grasper jaws and to release the Detachable Grasper from the Delivery/Retrieval Shaft. The Magnetic Grasper Device can be used for mobilization in the same manner as a conventional tissue grasper, or its Detachable Grasper can be released and used with the external Magnetic Controller. When the Detachable Grasper is released from the Delivery/Retrieval Shaft, the Delivery/Retrieval Shaft can be removed and mobilization of the tissue can be achieved through the magnetic attraction between the Detachable Grasper and the external MC. This access port is therefore available for use with other surgical tools. When the procedure is completed, the Delivery/Retrieval Shaft may be reinserted to retrieve the Detachable Grasper.

5. INDICATION FOR USE

The Magnetic Surgical System is designed for grasping the liver and the tissue surrounding the crus of the diaphragm and retract the liver in bariatric and/or hiatal hernia procedures to facilitate access to and visualization of the surgical site (**Figure 3**).

LVT009 Revision: B Date: 19 Jun 24	CONFIDENTIAL	Page 14 of 39
This document contains proprietary and confidential information of Levita Magnetics.		
Do not copy, dis tribute, or share with others without prior written authorization from Levita Magnetics.		

[figure not shown]

Figure 3. Intended Use

6. STUDY PURPOSE AND OBJECTIVE

The purpose of this study is to evaluate the safety and effectiveness of the Levita Magnetic Surgical System Version 2 in patients undergoing bariatric and/or hiatal hernia procedures.

7. STUDY ENDPOINTS

The following endpoints will be evaluated in all subjects who undergo bariatric and/or hiatal hernia procedures using the Magnetic Surgical System.

7.1 Safety Outcomes

All adverse events will be captured and reported. Adverse events will be further summarized by relatedness to the device and/or procedure, seriousness and level of severity.

7.2 Feasibility Outcomes

Ability to adequately mobilize the liver to achieve an effective exposure of the target tissue. Adequate mobilization is not achieved if it is necessary to use another liver retractor during the procedure.

7.3 Other Assessments

- Operative time.
- Time spent in the Post Anesthesia Care Unit (PACU).
- Length of stay (LOS) (time from admittance to post-anesthesia care unit until hospital discharge).

LVT009 Revision: B Date: 19 Jun 24	CONFIDENTIAL	Page 15 of 39
-		

- Conversion rate (conversion to an open procedure due to inadequate MSS performance).
- Estimated blood loss.
- Device malfunctions.

8. STUDY DESIGN

8.1 Overview

This is a prospective, multicenter, single-arm, open label study designed to assess the safety and effectiveness of the Levita Magnetic Surgical System: Extended Magnetic Grasper Device in bariatric and/or hiatal hernia procedures.

8.2 Sample Size and Number of Centers

The study will be conducted at up to three (3) study sites with a target maximum of 30 subjects in which the Levita Magnetic Surgical System is used for liver mobilization.

8.3 Study Duration

Enrollment of subjects in this study is anticipated to take up to 6 months. Clinical follow-up evaluations will be conducted at discharge, and 7 and 30 days following surgery. The total study duration is expected to be approximately 7 months.

9. STUDY PROCEDURES

9.1 Subject Eligibility, Pre-Screening, and Exclusions

All subjects presenting for elective bariatric and/or hiatal hernia procedures are potential candidates and will be screened for eligibility. A Screening/Enrollment Log will be provided to the study sites to maintain a cumulative tracking of all screened subjects.

Subjects must meet all study entrance criteria for enrollment in the clinical study. Reasons for screening failure(s) will be documented.

9.1.1 Inclusion Criteria

Subjects must meet ALL of the following inclusion criteria to be eligible for participation in the study:

- At least 18 years of age.
- Scheduled to undergo elective bariatric and/or hiatal hernia procedures.
- Willing and able to provide a written Informed Consent Form (ICF) to participate in the study prior to any study required procedures.

LVT009 Revision: B Date: 19 Jun 24	CONFIDENTIAL	Page 16 of 39
This document contains p	roprietary and confidential informatio	of Levita Magnetics.

9.1.2 Exclusion Criteria

Subjects must be EXCLUDED from participation in this study if ANY of the following exclusion criteria are met:

- Individuals with pacemakers, defibrillators, or other electromedical implants.
- Individuals with ferromagnetic implants.
- American Society of Anesthesiologists (ASA) score of III or IV.
- Significant comorbidities: cardiovascular, neuromuscular, chronic obstructive pulmonary disease, and urological disease (renal failure).
- Clinical history of impaired coagulation confirmed by abnormal blood tests.
- Individuals has signs of hepatic abnormality (e.g.: cirrhosis, liver failure, increase in liver enzymes, etc.).
- Anatomical abnormality or disease of intended target tissue noted after initiation of index procedure that would prevent device use.
- Pregnant or wishes to become pregnant during the length of study participation.
- Individual is not likely to comply with the follow-up evaluation schedule.
- Participating in a clinical trial of another investigational drug or device.
- Prisoner or under incarceration.

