11. STATISTICAL SECTION

11.1 Statistical Methods

Data collected in the study will be presented using various descriptive statistics. Descriptive summaries will be the basis of study reports to generate an overall summary of the safety and effectiveness for the device.

Descriptive tables will be produced for baseline characteristics including demographics and medical history.

Missing data on study endpoints will be described.

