11.7 Interim Analysis

Interim analysis plays a crucial role in ensuring the ongoing safety and efficacy of the trial. The interim analysis will involve an evaluation of accumulated data after 15 subjects to assess the predefined endpoints.

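### Subjects excluded during surgery because the device could not be used appear to drop out of the only feasibility rate, and section 11 does not commit to reporting them

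*Combined protocol and SAP*

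**What the plan says.** One exclusion criterion in section 9.1.2 can be judged only once the operation is under way: "Anatomical abnormality or disease of intended target tissue noted after initiation of index procedure that would prevent device use". Under section 9.2, a participant counts as enrolled only after consent and after the inclusion and exclusion criteria have been met.

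The analysis population has to be read from two other places. Section 7 states: "The following endpoints will be evaluated in all subjects who undergo bariatric and/or hiatal hernia procedures using the Magnetic Surgical System". Section 8.2 sets a "target maximum of 30 subjects in which the Levita Magnetic Surgical System is used for liver mobilization". Neither says at what moment use begins.

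Section 7.2 gives a single feasibility outcome: "Ability to adequately mobilize the liver to achieve an effective exposure of the target tissue". Needing another liver retractor counts as failure.

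On recording, section 9.1 provides a log of all screened subjects and says "Reasons for screening failure(s) will be documented". Section 9.7 documents reasons for early discontinuation, section 9.3 includes video of the procedure, and section 14.1.1 requires every adverse event to be recorded.

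On reporting, section 11 is descriptive and names no feasibility denominator. Section 11.1 says "Missing data on study endpoints will be described". Section 11.3 says all adverse events are reported, while section 11.4 ties this to a safety population that is not defined. Section 11.7 adds: "The interim analysis will involve an evaluation of accumulated data after 15 subjects to assess the predefined endpoints".

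**The concern.** The exclusion trigger, that the device could not be used, lies close to the outcome, which is whether the device could do its job. The decision is made during an open-label operation, and the documents describe no independent review of it. A subject excluded at that point may go on to need another retractor, which is the failure event in section 7.2, without entering the rate.

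This matters because it is the only feasibility outcome, there is no comparator, and section 12.4 says the results may support a regulatory submission. A single-arm descriptive rate can be interpreted only if its denominator is known. Two different quantities are possible: success among subjects in whom the device was used, and success among all procedures started. Unless the number excluded stands beside the result, a reader cannot tell how far apart they are. The same holds at the interim look.

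**Working it through.** **Step 1: follow an excluded subject through the text.**
- 9.1.2: surgery has started, a finding would prevent device use, and the subject is excluded.
- 9.2: the exclusion criteria must be satisfied for enrolment, so the subject is not enrolled.
- 8.2: the device is not used, so the subject does not count towards 30.
- 7: the procedure does not use the system, so the endpoints are not evaluated.
- 11.1: missing endpoint data are described, but a subject removed by an eligibility rule is not clearly a subject with missing data.

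The exit from the rate is therefore an inference from four sections, and nothing in section 11 contradicts it.

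**Step 2: direction.** Let n be the number of device-used subjects, s the successes among them, and k the intra-operative exclusions. A procedure without device use cannot be a success for the device, so the numerator is s either way. The device-used rate is s/n and the all-started rate is s/(n + k). Since k is at least 0, s/n is never smaller, and the two are equal when k = 0.

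**Step 3: size.** The plan gives no feasibility rate, target or exclusion frequency, so there is no figure of its own to reproduce. The count of 30 comes from section 8.2; s and k are assumptions. Intervals are exact (Clopper-Pearson), two-sided 95%. For s = n = 30 the lower limit is 0.025^(1/30) = 88.4%. Each exclusion is counted as mobilization not achieved.

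| k | No failure among 30 uses | One failure among 30 uses |
|---|---|---|
| 0 | 30/30 = 100% (88.4 to 100) | 29/30 = 96.7% (82.8 to 99.9) |
| 1 | 30/31 = 96.8% (83.3 to 99.9) | 29/31 = 93.5% (78.6 to 99.2) |
| 2 | 30/32 = 93.8% (79.2 to 99.2) | 29/32 = 90.6% (75.0 to 98.0) |
| 3 | 30/33 = 90.9% (75.7 to 98.1) | 29/33 = 87.9% (71.8 to 96.6) |
| 5 | 30/35 = 85.7% (69.7 to 95.2) | 29/35 = 82.9% (66.4 to 93.4) |

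As the plan reads, the k = 0 row would be reported whatever k was. The first exclusion costs 100 − 96.8 = 3.2 points when there are no failures.

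**Step 4: alternative count.** If the 30 were procedures started, with three excluded and the rest successful, the device-used rate would be 27/27 = 100% (87.2 to 100), against 27/30 = 90.0% (73.5 to 97.9) over all started.

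**Step 5: interim.** Section 11.7 does not say whether its 15 subjects are device-used. Assuming that they are and that all succeed, 15/15 = 100% (78.2 to 100) becomes 15/16 = 93.8% (69.8 to 99.8) with one exclusion, a drop of 6.2 points.

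**The case against.** The strongest reply is that the plan already has a target. Sections 7 and 8.2 point to subjects in whom the system is used, and a rate in anatomically suitable patients is legitimate. This stands: the target is implied, and the request is to make its boundary explicit and show what lies outside it.

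A reader might infer that failed attempts can be relabelled as exclusions, so that the rate is inflated by design. The documents do not support that. Section 9.1.2 requires an anatomical abnormality or disease; poor device performance is not a ground. Once the system is used, section 7 keeps the subject in, and section 7.2 makes another retractor a failure. What remains open is only the moment at which use starts.

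A reader might also infer that these cases vanish from the record. They do not: the log, the discontinuation reasons, the video and the adverse event forms would capture them, and section 12.3 requires a final report. But recording is not a commitment to report.

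Finally, the exclusion counts above are hypothetical, scoring every exclusion as a failure is harsh, and the plan sets no performance goal and plans no confidence intervals. All of this is right, and it limits the weight of the point.

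**Conclusion.** The point holds as a minor one. Sections 7, 8.2, 9.1.2 and 9.2 together take subjects excluded during surgery out of both the count of 30 and the feasibility rate. The start of use is undefined, and section 11 does not undertake to report these subjects.

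The size cannot be known from the documents. It is zero with no exclusions. Under the assumption that all 30 device-used procedures succeed and each exclusion counts as not achieved, one exclusion moves 100% to 96.8% and the lower limit from 88.4% to 83.3%; three move them to 90.9% and 75.7%. These all-started figures are lower bounds, because a genuine anatomical exclusion need not be a device failure. No formal decision changes, because the analysis is descriptive.

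**What to change.** 1. In section 7, for analysis counting only, name an observable step (for example, introduction of the grasper) from which a subject stays in the feasibility denominator. Apply the same rule at the interim look in section 11.7. This places no limit on surgical decisions.
2. In section 11, commit to reporting the number of intra-operative exclusions, the reasons, and any adverse events in these subjects. Beside the device-used rate, add a sensitivity rate over all procedures started that counts the exclusions as mobilization not achieved, with an exact 95% interval and labelled a lower bound.

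The cost is a few sentences, one disposition line, one table row and possibly one CRF field for the chosen step. The downside is that the sensitivity rate may be lower and counts genuine anatomical exclusions against the device, which is why the label is needed.
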